### 7. Measurement of Outcomes

# 7.1 Primary Outcome

167

168

171

172

173

174

175

176

The primary outcome is the changes in AHRS scores from baseline to posttreatment as well as follow-up.

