# **8. Sample Size Calculation**

The sample calculation is based on the AHRS, which is our study's primary outcome. According to a previous meta-analysis, which verified an efficacy favoring active low-frequency vs. sham rTMS with an effect size of 0.76 in the treatment-resistant AVH  $^{12}$ . Setting a power of 80% and a 2-tailed  $\alpha$  level of 5% for assessing AVH improvement, a sample size of 30 participants per group will be required. Additionally, a 10% attrition rate is considered, and the total sample size will be 66 participants.

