# 10. Statistical Analysis

We will use the IBM SPSS Statistics version 23.0 for statistical analyses. For the primary outcome and all continuous secondary outcomes, we will use linear mixed-effects models to test the treatment efficacy. Time, treatment group, and time-by-treatment interaction will be included in the model as fixed effects. The individual participant intercept will be included in the model as random effects. For the binary outcomes of treatment response, we will use the Chi-squared test or Fisher exact test to compare between groups. P values are 2-sided, and P < .05 will be considered statistically significant. Effect sizes will be calculated as Cohen's d and odds ratios for continuous and binary outcomes, respectively. We also provided the number needed to

- 218 treat (NNT), to assess the effectiveness of a clinical intervention . The missing data
- will be addressed using the multiple imputations method.

221 Reference:

- Sommer, IE, Slotema, CW, Daskalakis, ZJ, et al. The treatment of hallucinations in
  schizophrenia spectrum disorders. Schizophr Bull 2012;38(4):704-714.
- Andreasen, NC, Flaum, M. Schizophrenia: the characteristic symptoms. Schizophr
  Bull 1991;17(1):27-49.
- Goghari, VM, Harrow, M, Grossman, LS, et al. A 20-year multi-follow-up of
  hallucinations in schizophrenia, other psychotic, and mood disorders. Psychol Med
  229 2013;43(6):1151-1160.
- 230 4. Shergill, SS, Murray, RM, McGuire, PK. Auditory hallucinations: a review of psychological treatments. Schizophr Res 1998;32(3):137-150.
- Hor, K, Taylor, M. Suicide and schizophrenia: a systematic review of rates and risk
  factors. J Psychopharmacol 2010;24(4 Suppl):81-90.

- 243 9. Slotema, CW, Blom, JD, de Weijer, AD, et al. Can low-frequency repetitive

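### AHRS change to week 2 and to week 6 are both primary, no deciding visit or model term is named, and the sample size covers one comparison, so the stated 5% error and 80% power cannot be confirmed

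*Protocol*

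**What the plan says.** Protocol Section 7.1 defines the primary outcome in one sentence: "The primary outcome is the changes in AHRS scores from baseline to posttreatment as well as follow-up". The post-treatment visit is week 2 and the follow-up visit is week 6 (Section 3). Neither is put ahead of the other.

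Section 10 analyses this outcome with a linear mixed model: "Time, treatment group, and time-by-treatment interaction will be included in the model as fixed effects". For the covariance it says: "The individual participant intercept will be included in the model as random effects". The decision threshold is general: "P values are 2-sided, and P < .05 will be considered statistically significant". The section does not say which term or visit contrast decides efficacy, whether one visit or both must succeed, or whether the visits are tested in order.

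Section 8 uses one effect size, taken from a meta-analysis of "active low-frequency vs. sham rTMS with an effect size of 0.76", with 80% power and two-sided 5%. It concludes that "a sample size of 30 participants per group will be required" and, after attrition, plans 66 in total. It names no visit for that effect.

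**The concern.** These three sections have to fit together, because the error rate and power of a trial belong to its decision rule. Section 7.1 offers two comparisons, Section 10 offers several tests of them, and Section 8 calculates power for one comparison. The text allows at least four rules: either visit, both visits, the 2-df interaction, or the treatment main effect. They have different error rates and power, and only some deliver what Section 8 promises.

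The trial's main conclusion is at stake. If week 2 is positive and week 6 is not, or the reverse, this document does not say whether the hypothesis in Section 2 has been confirmed. Unless a rule is fixed before unblinding, it could be picked once the results are known.

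**Working it through.** **Inputs from the protocol.** Standardised effect d = 0.76, power 80%, two-sided α = 5% and n = 30 per arm (Section 8); two primary visits (Section 7.1); random-intercept mixed model (Section 10).

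**Input not in the protocol.** The correlation ρ between the two change contrasts. Under a random intercept with independent residuals of variance σ², the two changes from baseline share the baseline residual. Each change has variance 2σ² and their covariance is σ², so ρ = σ²/2σ² = 0.5. I take 0.5 as the value the model implies and show the range up to 0.8 as an assumption.

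**Step 1. Reproduce Section 8.** Normal approximation: n = 2(1.96 + 0.84)²/0.76² = 27.1, so 28 per arm. The two-sample t test needs 28.2, so 29. The stated 30 is close to this and gives 82.5% power by the t test (83.7% by the normal approximation). The figure is sound for one comparison.

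**Step 2. Separate tests at .05.** Treat the two test statistics as bivariate normal with correlation ρ. Each has mean 0.76 × √(30/2) = 2.94 under the planned effect and 0 under the null. The power figures in this step compare with the 83.7% in Step 1.

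| ρ | Type I error if either visit suffices | Power if both are required, d = 0.76 at each | n per arm for 80% with both required |
|---|---|---|---|
| 0.5 | 9.1% | 73.9% | 34 |
| 0.7 | 8.4% | 76.1% | 33 |
| 0.8 | 7.8% | 77.5% | 32 |

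Even at ρ = 0.9 the two figures are 7.0% and 79.3%.

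**Step 3. One 2-df time-by-treatment interaction test.** Type I error is 5%. Power comes from a noncentral F with 2 and 116 df and noncentrality 15 × d′R⁻¹d, where d holds the two visit effects and R is their correlation matrix. With 0.76 at both visits this is 15 × 0.76² × 2/(1 + ρ), which is 11.55 at ρ = 0.5. The week-6 effects of 0.50 and 0.38 are my assumptions, to show what happens if part of the effect is lost four weeks after the last session.

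| ρ | week-6 d = 0.76 | week-6 d = 0.50 | week-6 d = 0.38 |
|---|---|---|---|
| 0.5 | 86.1% | 75.7% | 74.2% |
| 0.7 | 81.3% | 74.4% | 77.6% |
| 0.8 | 78.9% | 76.7% | 83.7% |

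Under the planned effect this test meets 80% at ρ = 0.5 and 0.7 and narrowly misses it at 0.8. With a smaller week-6 effect the range is 74% to 84%. A significant result says that the profiles differ, not at which visit.

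**Step 4. Treatment main effect.** This averages the arm difference over all modelled visits. If baseline is one of three visits and the effect is δ at the other two, the term estimates (0 + δ + δ)/3 = 0.67δ. Randomised arms have no expected difference at baseline, so the term understates the effect.

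**Step 5. Fixed order.** Testing week 2 at two-sided 5%, and week 6 only if week 2 is significant, holds 5% error overall and keeps 82.5% power for week 2. The chance that both are significant is then the both-visits figure in Step 2.

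**The case against.** A reader might infer from two unranked primary visits that the 5% error rate or the 80% power must fail whatever the analysis. The documents do not support that. Section 10 specifies one model containing the interaction, and a single 2-df test of it is a natural reading. That test holds 5% and, with 0.76 at both visits and the correlation the model implies, has about 86% power. A fixed-order reading would also hold both figures. Nor does Section 10 say that each visit is tested separately at .05; it states only a general threshold. This objection stands and limits the point to what follows under each reading.

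A reader might also infer heavy power loss from a fading week-6 effect. Section 8 gives only one value, 0.76, so any smaller week-6 effect is an assumption, and even then the interaction test does not fall below 80% in every case (84% at correlation 0.8 with 0.38).

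Finally, a statistical analysis plan not shown here may name the contrast and the multiplicity rule, so it cannot be said that the choice is still open. That does not remove the point. The two-visit primary outcome and the one-comparison sample size are both set in the protocol, and a later rule requiring both visits, or splitting α, would no longer match Section 8.

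**Conclusion.** The point holds in limited form. The protocol makes two unranked visits primary, names no deciding visit or term, and sizes the trial for one comparison. The stated 5% and 80% therefore cannot be confirmed from it. Under the two separate-test readings one of them fails: error of 9.1% to 7.8% if either visit suffices, or power of 74% to 78% if both are required. These figures rest on 30 evaluable patients per arm, d = 0.76 at both visits for power, and a correlation of 0.5 to 0.8.

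The interaction test is an adequate rule under the planned effect if the correlation is not too high, but the protocol does not adopt it and it leaves the visit unidentified. Because the gap concerns the primary conclusion and costs little to close, it should be fixed before unblinding.

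**What to change.** In Sections 7.1 and 10, name one decisive contrast. The preferred choice is the between-arm difference in AHRS change at week 2, estimated from the mixed model and tested at two-sided 5%. Test week 6 at 5% only if week 2 is significant. State that the treatment main effect does not decide success. In Section 8, say that d = 0.76 and the 80% power refer to the named contrast; 30 per arm then stands.

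The choice of visit belongs to the sponsor. If it prefers week 6 first, both visits required, or the 2-df interaction, it should state that rule and restate the power. For example, requiring both visits needs about 34 per arm at correlation 0.5, before attrition, with 0.76 at each. Allowing either visit needs a split α: at .025 each, power per visit at 30 per arm is 73.8%, and about 35 per arm restores 80%.

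The preferred fix costs wording only, with no extra patients or visits. The downside is small: one visit loses co-primary status, and a week-6 claim depends on week 2 succeeding.

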# 7.2 Secondary Outcomes

Secondary outcomes measures will include: 1) the changes from baseline to post-treatment and follow-up in the PANSS, HAMA and HAMD score; 2) the number of responders at post-treatment and follow-up (responder is defined as  $\geq$ 25% reduction from baseline in AHRS and PANSS total scores); 3) the adverse events and blinding integrity.

The flow chart for each patient is shown below (Table 1).

### 178 **Table 1.** Schedule of Events

|                     | Screening and     | Post-treatment visit | Follow-up visit |
|---------------------|-------------------|----------------------|-----------------|
| Assessments         | baseline (Week 0) | (Week 2)             | (Week 6)        |
| Inclusion/exclusion | ×                 |                      |                 |
| criteria            | *                 |                      |                 |
| Informed consent    | ×                 |                      |                 |
| Randomization       | ×                 |                      |                 |
| Demographic data    | ×                 |                      |                 |
| MRI scan            | ×                 | ×                    |                 |
| RMT                 | ×                 |                      |                 |
| AHRS                | ×                 | ×                    | ×               |
| PANSS               | ×                 | ×                    | ×               |

| HAMA                     | × | × | × |
|--------------------------|---|---|---|
| HAMD                     | × | × | × |
| Adverse events record    |   | × | × |
| Blind integrity evaluate |   |   | × |

Abbreviations: MRI, magnetic resonance imaging; RMT, resting motor threshold; AHRS, Auditory Hallucination Rating Scale; PANSS, Positive and Negative Syndrome Scale; SAPS, Scale for Assessment of Positive Symptoms; SANS, the Scale for Assessment of Negative Symptoms; HAMA, Hamilton Anxiety Rating Scale; HAMD, Hamilton Depression Rating Scale.

# **8. Sample Size Calculation**

The sample calculation is based on the AHRS, which is our study's primary outcome. According to a previous meta-analysis, which verified an efficacy favoring active low-frequency vs. sham rTMS with an effect size of 0.76 in the treatment-resistant AVH  $^{12}$ . Setting a power of 80% and a 2-tailed  $\alpha$  level of 5% for assessing AVH improvement, a sample size of 30 participants per group will be required. Additionally, a 10% attrition rate is considered, and the total sample size will be 66 participants.

# 9. MRI Parameters

The structural and resting-state functional MRI data for each patient at baseline. Structural and functional MRI data will be acquired utilizing a 3.0 T scanner (Discovery 750; GE Healthcare, Milwaukee, WI, USA) at the University of Science and Technology of China (Hefei, Anhui Province). Specifically, functional images (comprising 217 volumes) are acquired through a single-shot gradient-recalled echo

planar imaging sequence (repetition/echo time: 2400/30 ms; flip angle:  $90^{\circ}$ ). Images of 46 transverse sections (field of view:  $192 \times 192$  mm2; in-plane matrix:  $64 \times 64$ ; section thickness: 3 mm without intersection gap) are acquired in parallel to the anteroposterior commissure line. Subsequently, high spatial resolution T1-weighted anatomic images will be obtained in the sagittal orientation employing a magnetization-prepared rapid gradient-echo sequence (repetition/echo time: 8.16/3.18 ms; flip angle:  $12^{\circ}$ ; field of view:  $256 \times 256$  mm2;  $256 \times 256$  matrix; section thickness: 1 mm, without intersection gap; voxel size:  $1 \times 1 \times 1$  mm3; 188 sections). We will employ foam fillers and earplugs to minimize head motion and diminish scanner noise during the scanning phase. Participants are instructed to keep their eyes closed and maintain a state of rest without falling asleep while acquiring images.

# 10. Statistical Analysis

We will use the IBM SPSS Statistics version 23.0 for statistical analyses. For the primary outcome and all continuous secondary outcomes, we will use linear mixed-effects models to test the treatment efficacy. Time, treatment group, and time-by-treatment interaction will be included in the model as fixed effects. The individual participant intercept will be included in the model as random effects. For the binary outcomes of treatment response, we will use the Chi-squared test or Fisher exact test to compare between groups. P values are 2-sided, and P < .05 will be considered statistically significant. Effect sizes will be calculated as Cohen's d and odds ratios for continuous and binary outcomes, respectively. We also provided the number needed to

- 218 treat (NNT), to assess the effectiveness of a clinical intervention . The missing data
- will be addressed using the multiple imputations method.

221 Reference:

- Sommer, IE, Slotema, CW, Daskalakis, ZJ, et al. The treatment of hallucinations in
  schizophrenia spectrum disorders. Schizophr Bull 2012;38(4):704-714.
- Andreasen, NC, Flaum, M. Schizophrenia: the characteristic symptoms. Schizophr
  Bull 1991;17(1):27-49.
- Goghari, VM, Harrow, M, Grossman, LS, et al. A 20-year multi-follow-up of
  hallucinations in schizophrenia, other psychotic, and mood disorders. Psychol Med
  229 2013;43(6):1151-1160.
- 230 4. Shergill, SS, Murray, RM, McGuire, PK. Auditory hallucinations: a review of psychological treatments. Schizophr Res 1998;32(3):137-150.
- Hor, K, Taylor, M. Suicide and schizophrenia: a systematic review of rates and risk
  factors. J Psychopharmacol 2010;24(4 Suppl):81-90.

- 243 9. Slotema, CW, Blom, JD, de Weijer, AD, et al. Can low-frequency repetitive

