# 3. Study Design

We will conduct a single-site, randomized, double-blinded, placebo-controlled clinical trial with two arms. The eligible patients with schizophrenia will be recruited through posted flyers and physician referrals from Anhui Mental Health Center (Hefei, China). In the screening phase, inclusion and exclusion criteria are investigated. Patients who meet the inclusion criteria will provide their written informed consent to participate and be randomly assigned to one of the groups to receive either active or sham cTBS treatment. Involved patients, clinical raters, and all personnel responsible for the clinical care of patients remain blinded to the allocated condition. Only rTMS administrators have access to the randomization list, but they have minimal contact with the patients and no role in assessing AVH. After the inclusion and randomization processes, patients will undergo three daily sessions of cTBS treatment for 2 weeks,

with assessments scheduled at three different visits: baseline (week 0), post-treatment (week 2), and a follow-up visit (week 6). Baseline assessments are conducted the day before the first cTBS session. Post-treatment and follow-up assessments are conducted one day and four weeks after the last cTBS session, respectively. The Auditory Hallucination Rating Scale (AHRS), the Positive and Negative Syndrome Scale (PANSS), the Hamilton Anxiety Rating Scale with 14 items (HAMA), and the Hamilton Depression Rating Scale with 17 items (HAMD) are assessed by a trained rater at baseline, post-treatment), and follow-up visit. These scales are applied to assess the severity of AVH and other symptoms. Furthermore, demographic data, structure magnetic resonance imaging (sMRI) and functional magnetic resonance imaging (fMRI) data are collected at baseline. The sMRI data will be used to navigate stimulation in real-time. The specific trial procedures are presented in Figure 1.

**Figure 1. Schematic representation of the trial procedures.** A, The trial consists of a 2-week rTMS treatment and three assessment visits at week 0, week 2, and week 6 (top). The clinical symptoms assessments include AHRS, PANSS, HAMA, and HAMD. B, The rTMS using continuous theta-burst stimulation (cTBS) paradigm will be performed with three daily sessions. The stimulation target on the

- 82 scalp will be navigated using Brainsight neuro-navigation software and individual structural MRI of

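### The primary mixed model has no baseline AHRS term: the analysis is valid, but less precise than the data already collected would allow

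*Protocol*

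**What the plan says.** Section 7.1 defines the endpoint: "The primary outcome is the changes in AHRS scores from baseline to posttreatment as well as follow-up". Section 10 sets one model for this and for PANSS, HAMA and HAMD: "For the primary outcome and all continuous secondary outcomes, we will use linear mixed-effects models to test the treatment efficacy". Its terms are given: "Time, treatment group, and time-by-treatment interaction will be included in the model as fixed effects". The random part is one term: "The individual participant intercept will be included in the model as random effects".

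AHRS is rated at week 0 in every participant (section 3 and Table 1), and section 3 fixes when: "Baseline assessments are conducted the day before the first cTBS session". No section enters baseline AHRS as a covariate or makes the two arms share a baseline mean.

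Section 8 plans 30 patients per group and 66 in total, for 80% power at a two-sided 5% level, "with an effect size of 0.76 in the treatment-resistant AVH". It does not say whether that figure is in SDs of the score or SDs of the change.

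**The concern.** Randomisation makes the true baseline means of the two arms equal. A model with group and time-by-group effects over weeks 0, 2 and 6 still estimates a separate baseline mean for each arm. The treatment effect then becomes a simple difference in change from baseline, which subtracts the whole baseline value even when baseline predicts the later score only in part. Adjusting for baseline removes only the part that is predictive, and is usually more precise.

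Section 10 does not say outright that week 0 is among the responses, although that is the natural reading of a time-by-group model with three visits. If the responses are instead the changes at weeks 2 and 6, the model still contains no baseline term.

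At stake is avoidable imprecision in a trial planned around 60 evaluable patients. Because section 10 names its fixed effects, this is a choice the protocol makes, not a detail it leaves open.

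**Working it through.** **Inputs from the protocol.** Effect size 0.76, 30 per group, power 80%, two-sided 5% level, 10% attrition, total 66 (sections 8 and 10).

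**Inputs assumed.** The correlation rho between baseline and follow-up AHRS, and the ratio k of follow-up SD to baseline SD. The protocol gives neither, so ranges are shown.

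**1. The plan's own sample size.** For a standardised difference of 0.76, the normal approximation gives 28 per group and the noncentral t gives 29 (power 81.2%). At 30 per group the noncentral t gives 82.5%. For attrition, 60 × 1.1 = 66. The stated figures reproduce closely enough.

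**2. What the stated model estimates.** The model was fitted to one simulated data set (30 per arm, three visits, rho 0.5, no missing data). The week-2 interaction contrast was -0.6291, the same as the raw difference in mean change, with SE 0.229. With a common baseline mean imposed on the same data, the SE was 0.199. The variance ratio is (0.199/0.229)² = 0.755.

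**3. Variance, equal SDs (k = 1).** In units of the score variance:
- change score: 2(1 - rho)
- baseline-adjusted: 1 - rho²
- ratio, adjusted to change: (1 + rho)/2

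This gives 0.65, 0.75 and 0.85 at rho 0.3, 0.5 and 0.7, and 0.95 at rho 0.9. Simulation with 10,000 replicates gave 0.655, 0.763 and 0.862 at the first three.

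**4. Variance, unequal SDs.** The ratio is k²(1 - rho²)/(1 + k² - 2·rho·k). At k = 1.25 it is:
- rho 0.3: 1.5625 × 0.91/1.8125 = 0.78
- rho 0.5: 1.5625 × 0.75/1.3125 = 0.89
- rho 0.7: 1.5625 × 0.51/0.8125 = 0.98

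The ratio reaches 1, meaning no gain, when rho·k = 1, for example k = 1.25 with rho 0.8. With k below 1 the gain is larger than in step 3: at k = 0.8 and rho 0.5 the ratio is 0.64 × 0.75/0.84 = 0.57.

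**5. Power at 30 per arm, 0.76 in SDs of change (k = 1, noncentral t).** The effective standardised difference after adjustment is 0.76/√((1 + rho)/2).

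| rho | Change score | Adjusted |
|---|---|---|
| 0.3 | 82.5% | 94.8% |
| 0.5 | 82.5% | 91.7% |
| 0.7 | 82.5% | 88.1% |

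**6. Power at 30 per arm, 0.76 in SDs of the score (k = 1, noncentral t).** The standardised differences are 0.76/√(2(1 - rho)) for change and 0.76/√(1 - rho²) adjusted.

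| rho | Change score | Adjusted |
|---|---|---|
| 0.3 | 68.7% | 85.9% |
| 0.4 | 75.2% | 88.5% |
| 0.5 | 82.5% | 91.7% |
| 0.6 | 89.9% | 95.1% |
| 0.7 | 96.2% | 98.2% |

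On this scale the change-score analysis reaches 80% at rho of about 0.47.

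**7. Cost of the extra term.** Steps 5 and 6 do not charge the adjusted analysis for estimating the baseline slope. Doing so lowers its power by less than one percentage point (85.2% instead of 85.9% at rho 0.3 in step 6).

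**The case against.** The strongest reply is that nothing here is an error. The endpoint is a change and the model tests a change. Under randomisation the contrast is unbiased and its type I error is kept. A more efficient valid model is a preference, and prognostic covariates are often settled in an analysis plan, which is not shown here. The first part stands and sets the weight of the point. The second is weakened because section 10 names the model terms.

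Four stronger readings are tempting, and the documents do not support them.

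- *The trial is underpowered.* This needs both 0.76 to be in SDs of the score and rho to be below about 0.47 (with equal variances). The protocol states neither. On the change scale the planned analysis has 82.5%, above its target.
- *Adjustment gains at every correlation below 1, by (1 + rho)/2.* That formula needs equal baseline and follow-up variances. A random intercept with one residual variance implies them, but the AHRS data may not follow. A larger follow-up SD is plausible because entry is restricted to frequent, medication-resistant hallucinations (section 4), which may narrow the baseline spread.
- *Chance baseline imbalance is a further harm.* With 33 per arm, a one-SD imbalance is √(2/33) = 0.246 score SDs and moves the change-score estimate by (1 - rho) × 0.246, or 0.07 to 0.17 SD for rho 0.7 to 0.3. But 2(1 - rho) - (1 - rho²) = (1 - rho)², so this is the variance loss of step 3 seen again and must not be added to it.
- *Baseline AHRS is thrown away.* It is used, by subtraction. It is only not used efficiently.

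**Conclusion.** The point holds as a free improvement in precision. The stated model has no baseline adjustment on either reading of its response variable. The planned test is valid, and the sample size of 30 per group is not shown to be wrong.

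The size of the gain depends on quantities the protocol does not give. For rho between 0.3 and 0.7, adjustment would cut the variance by 15% to 35% if the variances are equal, and by about 2% to 22% if the follow-up SD is 1.25 times the baseline SD. It would cut it by more if the follow-up SD is the smaller. The gain fades as rho approaches 1 under equal variances, and is nil where rho·k = 1. The exact identity with the raw difference in mean change assumes week 0 is a response and the data are complete. The lack of adjustment depends on neither.

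**What to change.** Replace the model statement in section 10. Take AHRS at weeks 2 and 6 as the responses, with fixed effects for treatment, visit, treatment-by-visit, baseline AHRS and baseline-by-visit. If week 0 is to stay among the responses, drop the treatment main effect so that the arms share one baseline mean and treatment enters only after baseline. State which form is used. Treat PANSS, HAMA and HAMD the same way, each with its own baseline.

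Fix this before unblinding, because an adjustment added later would look data-driven. It changes the model statement only: no extra visit, measurement or patient is needed, and the sample size can stay as it is.

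### A random intercept as the only stated covariance term gives every visit contrast one pooled standard error, which can understate the error of the week-6 change if correlation falls with time

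*Protocol*

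**What the plan says.** Protocol section 10 analyses the primary outcome and every continuous secondary outcome with a linear mixed model in SPSS. The fixed effects are time, treatment group and their interaction. On the covariance it says: "The individual participant intercept will be included in the model as random effects". It names no random slope, residual covariance structure or robust standard error. The test level is nominal: "P values are 2-sided, and P < .05 will be considered statistically significant".

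Protocol section 3 has "three assessment visits at week 0, week 2, and week 6", and places the two later ones as follows: "Post-treatment and follow-up assessments are conducted one day and four weeks after the last cTBS session, respectively". Protocol section 7.1 makes the AHRS change to both later visits the primary outcome, so the week-6 change belongs to the primary claim.

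**The concern.** A random intercept with independent, equal-variance residuals forces one variance at every visit and one correlation for each pair of visits. The change from week 0 to 2, from 0 to 6 and from 2 to 6 then all get the same standard error, taken from their average variance.

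The visits here are 2 and 4 weeks apart, and two scores usually agree less the further apart they are taken. If so, the change over the full 6 weeks varies more than that average and its standard error is too small. The claim most exposed is that a benefit persists four weeks after treatment ends. PANSS, HAMA and HAMD are analysed with the same model.

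**Working it through.** **The plan's own figure.** Inputs from Protocol section 8: "sham rTMS with an effect size of 0.76 in the treatment-resistant AVH", 80% power and two-sided 5%. The normal approximation gives n = 2 × (1.960 + 0.842)² / 0.76² = 15.70 / 0.5776 = 27.2, so 28 per arm. The noncentral t gives 29 (power 81.2%). The stated 30 per group is consistent with this (power 82.5% by t), and 60 × 1.10 = 66 gives the stated total. The sample size is not in dispute. The check below uses 30 per arm.

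**Formula.** Let Vjk be the variance of the change from week j to week k: SDj² + SDk² − 2 × rjk × SDj × SDk. With complete data, the random-intercept model estimates the variance of every change by the mean of V02, V06 and V26. The true week-6 type I error is therefore close to 2 × (1 − Φ(1.96 / √R)), with R = V06 / mean(V02, V06, V26). An error of 9% needs R = 1.34, and 10% needs R = 1.42.

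**Assumed inputs.** All SDs and correlations below are assumptions, because the protocol gives none. Correlations are listed as r02/r06/r26.

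| SDs; correlations | V02, V06, V26 | R | Week-6 error |
|---|---|---|---|
| equal; 0.6/0.6/0.6 (compound symmetry) | 0.8, 0.8, 0.8 | 1.00 | 5.0% |
| equal; 0.6/0.55/0.65 | 0.8, 0.9, 0.7 | 1.13 | 6.5% |
| equal; 0.6/0.5/0.6 | 0.8, 1.0, 0.8 | 1.15 | 6.8% |
| 5/7/8; 0.5/0.4/0.7 | 39, 57, 34.6 | 1.31 | 8.7% |
| 5/7/7; 0.5/0.4/0.8 | 39, 46, 19.6 | 1.32 | 8.8% |
| equal; 0.6/0.4/0.7 | 0.8, 1.2, 0.6 | 1.38 | 9.6% |
| equal; 0.8/0.64/0.8 | 0.40, 0.72, 0.40 | 1.42 | 10.0% |
| 1/1.25/1.5; 0.5/0.5/0.5 (rising SD only) | 1.31, 1.75, 1.94 | 1.05 | 5.6% |
| 1/1.3/1.1; 0.5/0.6/0.5 | 1.39, 0.89, 1.47 | 0.71 | 2.0% |

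For example, in the sixth row the mean is (0.8 + 1.2 + 0.6) / 3 = 0.867 and R = 1.2 / 0.867 = 1.38. The standard error is then 1 − 1/√1.38 = 15% too small.

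Simulated null trials at 30 per arm agree with the closed form to within about half a percentage point. A direct REML fit gave 9.8% for correlations 0.7/0.49/0.7 (1,000 trials) and 5.2% under compound symmetry (600 trials).

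**Other tests from the same model.**
- *Week 2.* Replacing V06 by V02 in R gives 3.8%, 6.4% and 4.1% for rows 4 to 6. Over all sets examined the week-2 error is often below 5%: about 3% with autoregressive decay by visit, and about 1% with decay by weeks elapsed. The highest value, 6.8%, occurs with equal SDs and 0.5/0.4/0.8.
- *Joint 2-df time-by-treatment test.* About 5% to 6% throughout.
- *Change scores as the dependent variable.* Only weeks 2 and 6 enter, so R = V06 / mean(V02, V06). Rows 4 to 6 give 57/48 = 1.19, 46/42.5 = 1.08 and 1.2/1.0 = 1.20, or 7.2%, 6.0% and 7.4%. Steeper decay gives more: row 7 has 0.72/0.56 = 1.29, or 8.4%.

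**With each contrast's own variance.** This is what an unstructured covariance uses with complete data. The week-6 error was 4.8% to 5.2% in all 18 covariance patterns of the main simulation.

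**Limit.** All of this assumes complete data. The planned multiple imputation was not simulated.

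**The case against.** Several objections have force.

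- **The protocol names no week-6 test.** It says only that the model tests efficacy. If efficacy is judged on the joint interaction, the error stays near nominal. This stands, and limits the point to the week-6 contrast. It does not remove the point, because section 7.1 counts the change to follow-up as primary and nothing confines inference to the joint test.
- **The model may be fitted to change scores.** Section 7.1 can be read that way. The excess is then smaller in the three sets compared, at about 6% to 7%.
- **The covariances are chosen by the analyst.** This is true. A reader might infer that the trial's type I error is 9% to 10%. The protocol does not support that: the figure is the top of a range that runs from 5% under compound symmetry through 6% to 7% under mild decay, and one pattern gives 2%.
- **Rising variance is not the cause.** A reader might blame scores that spread out after treatment, or a baseline narrowed by selection. With three visits, rising SDs alone give only 5.6%. The entry criterion in section 4 is a daily count of hallucinations, not an AHRS cut-off, so a narrowed AHRS baseline is only a conjecture.
- **The analysis plan is not shown.** It may add a residual structure, which would settle the matter. Even so, the protocol does more than leave the covariance open: it commits to a specific term that is restrictive when used alone.

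**Conclusion.** The point holds for the baseline-to-week-6 contrast. As written, the model gives that contrast a pooled standard error that is right only if its variance equals the average over the three pairs of visits. Its type I error is about 5% under compound symmetry, about 6% to 7% under mild decay of correlation (or, in the sets compared, if change scores are modelled), and up to about 9% to 10% under stronger decay with three visits. Falling correlation is the main driver.

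It would go too far to say that the P values are wrong without condition, or that the whole primary analysis is anticonservative. The week-2 test is often conservative, the joint test stays near nominal, and some patterns make the week-6 test conservative too. The size depends on AHRS covariances that the protocol does not give. This is a cheap improvement, not a flaw that undermines the trial.

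**What to change.** In Protocol section 10, replace the sentence on the random intercept. Specify an unstructured within-participant covariance across visits (the REPEATED statement in SPSS MIXED) with Satterthwaite degrees of freedom. Name the fallback if the model does not converge: a structure in which correlation falls with time and variances may differ, such as heterogeneous first-order autoregressive, or a separate baseline-adjusted analysis of change at each visit. Compound symmetry should not be the fallback, because it would bring the problem back.

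The cost is six covariance parameters in place of two (three if only the two change scores are modelled) and fewer degrees of freedom for each contrast. With complete data at 30 per arm, these are 58 instead of 116, which moves the critical value from about 1.98 to 2.00. Sample size, visits and patient burden do not change.
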